#### 6.6 STOPPING RULES

In order to allow periodic review of safety data to ensure safety and limit potential toxicity, enrollment shall be conducted in consecutive groups of 10 patients. The Principal Investigator (PI), Sub-Investigators, and the Moffitt Protocol Monitoring Committee (PMC) will be charged with reviewing safety data. Serious adverse events (SAEs) from this protocol will be reported to the IRB per their guidelines and concurrently to the PMC for review. Following the final treatment dose in Cycle 3 (Day 28 of Cycle 3) of the last patient in a group set of 10 patients, the PI and PMC will decide whether or not it is possible to proceed to enroll the next group of 10 patients. In order to ensure safety and limit toxicity for enrolled patients, dose modifications will be performed according to the schema described in Section 6.3.1. This trial will be continuously monitored by the PI and the research team as well as being reviewed for safety at the weekly Lymphoma Section Research Meeting. All serious and non-serious adverse events will be documented, managed with protocol-permitted dose reductions, followed until resolution or stabilization, and will also be reviewed by the PI, PMC and Sub-Investigators at the end of each group of 10 patients.

In the event that >20% of patients (i.e. 3 of 10 patients, 5 of 20 patients, 7 of 30 patients, etc.) discontinue therapy due to a treatment-related serious adverse event or immune mediated toxicity (e.g. transaminitis, pneumonitis, rash, or colitis), study accrual will be suspended pending further investigation, and will only be resumed at the recommendation of the PI, PMC and the Sub-Investigators.

In the event of one (1) death attributed to the study drug, study accrual will be suspended pending further investigation, and will only be resumed at the recommendation of the PI, PMC, and the Co-

Investigators. The PI, PMC, and the Sub-Investigators will have discretion to terminate the trial if an additional death occurs that can be attributed to the study drug.

# 7 STUDY MEDICATION OVERVIEW AND SAFETY

| 7.1 UMBRALISIB              |   |  |  |
|-----------------------------|---|--|--|
| Chemical Name:              | Umbralisib  |  |  |
| Other Names:                | TGR-1202  |  |  |
| Classification:             | Dual inhibitor o phosphatidylinositol-3-Kinase (PI3K) Delta and
Casein kinase-1 epsilon (CK-1 E)   |  |  |
| Formulation:                | See Investigator Brochure   |  |  |
| Mode of Action:             | Irreversibly inhibits activity of the Class I Delta isoform of PI3K   |  |  |
| How Supplied:               | 200 mg tablets  |  |  |
| Storage:                    | Store in a secured limited-access area between $20^{\circ}$ and $25^{\circ}$ C. Excursions permitted $15^{\circ}$ C to $30^{\circ}$ C.Do not freeze |  |  |
| Stability:                  | Expiration memorandums will be provided noting lot expiration dates. For questions about product expiry email [contact]            |  |  |
| Route of
Administration: | Oral  |  |  |
| Packaging:                  | Umbralisib is provided in HDPE bottles each containing 30 tablets and a silica gel canister as a desiccant.   |  |  |
| Availability:               | Umbralisib is available from TG Therapeutics.   |  |  |

#### 7.1.1 COMPREHENSIVE ADVERSE EVENTS AND POTENTIAL RISKS LISTS (CAEPRS)

The Investigator's Brochure (IB) is the primary source for safety information. The umbralisib IB includes a summary of adverse event data and discussion on potential risks that have been observed or may be predicted to occur with this study drug. Refer to the most recent IB, which is updated periodically, for current information on umbralisib.

7.1.1.1 VERY COMMON  $\geq 10\%$ 

- Blood and Lymphatic System Disorders: neutropenia
- Gastrointestinal Disorders: Diarrhea, Nausea, vomiting

# 7.1.1.2 GENERAL DISORDERS AND ADMINISTRATION SITE CONDITIONS: FATIGUE COMMON $\ge 2\%$ AND < 10%

- **Blood and Lymphatic System Disorders:** anemia, thrombocytopenia, leukocytosis, lymphocytosis
- Ear and Labyrinth Disorders: tinnitus

- **Eye Disorder:** vision blurred
- **Gastrointestinal Disorder:** constipation, abdominal pain, abdominal distension, dyspepsia, colitis, dry mouth
- General Disorders and Administration Site Conditions: pyrexia, oedema peripheral
- Infections and Infestations: pneumonia, oral candidiasis
- Injury Poisoning and Procedural Complication: contusion
- **Investigations:** weight decreased, alanine aminotransferase increased, aspartate aminotransferase increased, blood creatinine increased
- **Metabolism and Nutrition Disorders:** decreased appetite, dehydration, hyperglycaemia, hypokalaemia, hypophosphatemia
- Musculoskeletal and Connective Tissue Disorder: muscle spasms, pain in extremity
- Nervous System Disorders: dizziness, headache, dysgeusia, tremor
- Nervous System Disorders: dizziness, headache, dysgeusia, tremor
- **Psychiatric Disorders:** insomnia
- Respiratory, Thoracic and Mediastinal Disorders: cough
- Skin and Subcutaneous Tissue Disorders: rash maculo-papular, alopecia, night sweats, pruritus, rash

# 8 MEASUREMENT OF EFFECT

During the study period, all patients will be evaluated for response by CT or MRI within 14 days prior to Cycle 4, Day 1 for Cycle 3 assessment, and within 14 days prior to Cycle 13, Day 1 for Cycle 12 assessment, and at any other time point to confirm progression. The determination of response and progression will be based on iwCLL criteria (Hallek M, 2018).

Patients who fail to achieve a partial or complete response to umbralisib at the Cycle 3 assessment will discontinue study treatment. At that time, patients- will be provided appropriate options to receive established frontline therapy. Patients who demonstrate a partial or complete response will be treated until disease progression, unacceptable toxicity, or the end of the study.

Patients with a response should remain on study treatment until the occurrence of definitive disease progression, unacceptable toxicity, or withdrawal from the study due to investigator decision or other reasons. Patients who discontinue from study treatment (either for toxicity or physician choice) and have not progressed will continue to be followed for progression as per the protocol.

#### 8.1 METHOD OF ASSESSMENT

In addition to clinical examination, radiographic evaluation will be used in all patients enrolled. All baseline assessments to characterize disease will be performed within 30 days of Cycle 1, Day 1, prior to initiation of therapy. CT scan with iodinated IV contrast is the preferred method for radiographic tumor assessment. If iodinated contrast is contraindicated, a non-contrast chest CT coupled with a gadolinium-enhanced MRI of the abdomen, pelvis and neck is an acceptable substitute. Chest x-ray, ultrasound, endoscopy, laparoscopy, PET, radionuclide scans, or tumor markers will not be considered for response assessment.

For radiographic evaluations, the same method of assessment and the same technique (e.g.,

scan type, patient position, dose of contrast, injection/scan interval) should be used to characterize each identified and reported lesion at baseline and during study treatment and follow-up. However, if a patient is imaged without contrast at baseline, subsequent assessments should be performed with contrast, unless medically contraindicated.

All relevant clinical and radiographic information required to make each tumor status assessment must be made available for source verification.

#### 8.2 RESPONSE REVIEW

The review of radiographic and clinical data by the study investigators will be performed on an ongoing basis. De-identified images should be available if TG Therapeutics requests to confirm any objective response observed.

# 8.3 IDENTIFICATION AND MEASUREMENT OF TUMOR LESIONS AND ORGANOMEGALY

#### 8.3.1 TARGET LESIONS

At baseline, up to 6 lymph nodes should be selected as target lesions (if measurable disease is present) that will be used to quantitate the status of the disease during study treatment. Ideally, the target lesions should be located in disparate regions of the body. Only peripheral nodes need be selected as target lesions. However, it is optimal if mediastinal and retroperitoneal areas of disease are assessed whenever these sites are involved.

Target lesions should be measured and recorded at baseline and as per the study assessment schedule. The cross-sectional dimensions (the largest cross-sectional diameter, i.e., the LD × LPD) will be recorded (in cm) for each target lesion. The product of the perpendicular diameters (PPD) (in cm^2) for each target lesion and the sum of the products (SPD) (in cm^2) for all target lesions will be calculated and recorded. The baseline SPD will be used as references by which objective tumor response will be characterized during treatment. The nadir LD of individual lesions and the nadir SPD will be used as references by which CLL progression will be characterized. All LD and LPD diameters will be reported in centimeters and all PPDs and SPDs will be reported in centimeters squared.

A nodal mass may be selected as a measurable nodal target lesion if it is > 1.5 cm in the longest diameter (Hallek M, 2018).

Progressive disease will be determined using the 2018 iwCLL criteria. Transient increases of lymph node size during treatment with novel inhibitors may occur (Hallek M, 2018).

#### 8.3.2 SPLEEN AND LIVER

Both the spleen and liver will be assessed by CT/MRI scan and/or by physical examination (method of measurement should be consistent throughout study participation) at baseline and as per the study assessment schedule. The baseline and nadir values for the longest vertical dimension (LVD) of each organ will be used as reference to further characterize the objective tumor response of the measurable dimensions of the CLL during treatment. All spleen and liver

LVD measurements should be recorded in centimeters.

By imaging, the spleen will be considered normal if <13 cm using craniocaudal measurement (Hallek M, 2018).

There is no international consensus on the size of a normal liver (Hallek M, 2018). For the purpose of this trial, a decrease to  $\leq$  18 cm in the longest diameter on CT scan will be considered a normal liver. The iwCLL 2018 criteria will be utilized to determine the response.

### 8.3.3 NON-TARGET LESIONS

Any other measurable and abnormal nodal lesions not selected for quantitation as target lesions may be considered non-target lesions. In addition, non-measurable evidence of CLL such as nodal lesions with both diameters < 1.0 cm, extra-nodal lesions, bone lesions, leptomeningeal disease, ascites, pleural or pericardial effusions, lymphangitis of the skin or lung, abdominal masses that are not confirmed and followed by imaging techniques, cystic lesions, previously irradiated lesions, and lesions with artifacts may be considered as non-target disease.

The presence or absence of non-target disease should be recorded at baseline and as per the study assessment schedule. If present at baseline, up to 6 non-target lesions should be recorded. The non-target disease at baseline will be used as a general reference to further characterize regression or progression of CLL during assessments of the objective tumor response during treatment. Measurements are not required and these lesions should be followed as "present" or "absent".

#### 8.4 DEFINITIONS OF TUMOR RESPONSE AND PROGRESSION

Responses will be categorized as CR, PR, SD, or PD. Response criteria for this protocol will be per iwCLL 2018 criteria (see Appendix D). Response to therapy includes 2 groups of parameters that need to be documented. Group A assesses the lymphoid tumor load (CT) and constitutional symptoms; group B assesses the hematopoietic criteria. The hemataopoietic criteria will be evaluated using the lab testing on Cycle 4 Day 1 and Cycle 13 Day 1.

For the purpose of this study, the bone marrow biopsy response criterion will be calculated using the following formula:

Cellularity x % involvement of CLL= percent of response

If the reporting pathologist provides a range for B-cell or lymphocytic leukemia involvement (i.e.,80-85%), the higher number of the range will be used for the calculation.

The best overall response will be determined. The best overall response is the best response recorded from the start of treatment until disease/recurrence progression (taking as a reference for disease progression the smallest measurements recorded since treatment started). Where imaging data are available, these data will supersede physical examination data in determining tumor status.

#### 8.5 LYMPHOCYTOSIS DURING THERAPY

Upon initiation of umbralisib, a temporary increase in lymphocyte counts (i.e.,  $\geq$  50% increase from baseline and above absolute lymphocyte count of 5,000/mcL) may occur. The onset of isolated lymphocytosis usually occurs during the first few weeks of umbralisib therapy and usually resolves within three to four months. Patients with lymphocytosis should be continued on study drug until the occurrence of definitive disease progression (i.e., disease progression that is manifest by worsening CLL-related signs other than lymphocytosis alone), or the occurrence of another reason to discontinue study therapy.

## 9 STATISTICAL CONSIDERATIONS

#### 9.1 SAMPLE SIZE

This is a phase 2 study designed to assess the overall response rate (CR + PR) and progressionfree survival (PFS) of Umbralisib in treatment naïve patients with CLL. The primary endpoint is the overall response rate (ORR) from the time of treatment. The study will plan to enroll up to 40 subjects, and assuming 10% attrition, the study will have approximately 35 subjects remaining for analysis. Any subjects who are screen failures are not considered enrolled and may be replaced to meet the accrual goal. Enrollment is expected to be completed in approximately 18 months with 24 months follow up. The ORR for the standard of care is about 60%. We expect that Umbralisib treatment could lead to 80% ORR. A Simon 2-stage minimax design that differentiates ORRs of 0.60 (null hypothesis) and 0.80 (alternative hypothesis) will be used to assess treatment efficacy, with the probabilities of a type I error (falsely accepting a non-promising therapy) and type II error (falsely rejecting a promising therapy) both set at 0.10. Twenty seven patients will be accrued in the first stage of the study. If 18 or fewer patients have a response, then the study will be terminated and declared negative. If 19 or more patients have a response, then an additional 8 patients will be accrued to the second stage. At the conclusion of the study, if 25 or more patients have a response out of a total of 35 patients enrolled, the regimen will be considered worthy of further investigation.

## 9.2 GENERAL ANALYSIS CONVENTION

Unless otherwise stated, all analyses will be performed using SAS Version 9.2 or higher and all hypothesis tests will be conducted at a two-sided significance level of 0.05.

In general, summary tabulations will display the number of observations, mean, standard deviation, median, minimum, maximum, and appropriate percentiles for continuous variables, and the number and percentage by category for categorical data. Summaries will be presented. The data listings will include all available efficacy and safety data.

#### 9.3 STUDY POPULATIONS

Two study populations, intent-to-treat (ITT) and safety populations, are pre-defined for this study. The ITT population will include all enrolled patients who provide some efficacy assessments and the safety population will include all patients who take at least one dose of study medication. The efficacy analyses will be based on ITT population and the safety analyses will be based on the safety population.

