| Statistics | The study will plan to enroll up to 40 subjects, and assuming 10% attrition, there will be approximately 35 subjects remaining for analysis. Enrollment is expected to be completed in approximately 18 months with 24 months follow- up. The ORR for the standard of care is about 60%. We expect that Umbralisib treatment could lead to 80% ORR. A Simon 2-stage minimax design that differentiates ORRs of 0.60 (null hypothesis) and 0.80 (alternative hypothesis) will be used to assess treatment efficacy, with the probabilities of a type I error (falsely accepting a non-promising therapy) and type II error (falsely rejecting a promising therapy) both set at 0.10. Twenty seven patients will be accrued in the first stage of the study. If 18 or fewer patients have a response, then the study will be terminated and declared negative. If 19 or more patients have a response, then an additional 8 patients will be accrued to the second stage. At the conclusion of the study, if 25 or more patients have a response out of a total of 35 patients enrolled, the regimen will be considered worthy of further investigation. |
|------------|--|
|            | Safety will be examined on an ongoing basis while the study is being conducted.
Adverse events will be recorded as per CTCAE v5.0.  |

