| PDs    |                | Х         |        |              |          | Х              |  |           |            |            |
| Umbralisib 800 mg  |                |           |        |              | Daily    | 7 Days 1 – 28  |  |           |            |            |
| Bone Marrow Biopsy                            | Х              |           |        |              |          |                | Х  |           |            |            |
| AE Assessment  |                | Х         |        | Х            | Х        | Х              | Х  | Х         |            |            |

 Visit days and all related assessments and testing have +/- 1 day window in Cycle 1.

 Unless otherwise noted (i.e. CT scans), visit days and all related assessments and testing have +/- 3 day window in Cycles 2 - 6.

 Unless otherwise noted (i.e. CT scans), visit days and all related assessments and testing have +/- 7 day window for Cycles > 6.

 Serum virology to include HBsAg, HBc antibody, HCV antibody, CMV IgG and CMV IgM. If HBc antibody is positive, the subject must be evaluated for the presence of HBV DNA by PCR - See Appendix C. If HCV antibody is positive, the subject must be evaluated for the presence of HCV RNA by PCR. If the subject is CMV IgM positive, the subject must be evaluated for the presence of CMV DNA by PCR. CMV surveillance by PCR every 3 cycles while receiving study treatment. In addition, a final CMV test by PCR should be done upon treatment discontinuation.

 Baseline CT scan within 30 days prior to Cycle 1, Day 1; then within 14 days prior to Cycle 4, Day 1 for Cycle 3 assessment, and within 14 days prior to Cycle 13, Day 1 for Cycle 12 assessment. Additional scans may be requested at the discretion of the investigator at any other time point to confirm progression (all scans +/-14 days). CT imaging should be performed at EOT visit if it hasn't been completed within past 30 days.

 Serum pregnancy test within 3 days prior to starting treatment on Cycle 1, Day 1 for women of childbearing potential.

 Peripheral Blood Mononuclear Cells (PBMC) – Peripheral blood sample to be obtained pre-dose on C1D1, C2D1, C4D1, C7D1, C13D1 and at the time of disease progression, which may occur at any time point including at the End of Treatment visit or the End of Study visit.

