#### 9.7 EFFICACY ANALYSES

Each patient will be assigned to one of the following categories: 1) complete response, 2) partial response, 3) stable disease, 4) progressive disease, 5) early death from malignant disease, 6) early death from toxicity, 7) early death because of other cause, or 8) unknown (not assessable, insufficient data).

Many of the efficacy measures will be based on disease assessments. The best clinical response as well as disease progression will be determined by the treating investigator. Scans should be kept on file in cases where independent review or confirmation may be warranted. Definitive disease progression will be based on standard criteria (Hallek et al. 2018) occurring for any reason (e.g., increasing lymphadenopathy, organomegaly or bone marrow involvement; decreasing platelet count, hemoglobin, or neutrophil count; or worsening of disease-related symptoms) other than lymphocytosis.

During the study period, all patients will be evaluated for response by CT or MRI within 14 days prior to Cycle 4, Day 1 for Cycle 3 assessment, and within 14 days prior to Cycle 13, Day 1 for Cycle 12 assessment, and at any other time point to confirm progression. Patients who fail to achieve a partial or complete response to umbralisib at the Cycle 3 assessment will discontinue study treatment. At that time, patients- will be provided appropriate options to receive established frontline therapy. Patients who demonstrate a partial or complete response will be treated until disease progression, unacceptable toxicity, or the end of the study.

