#### 9.8 MISSING VALUE HANDLING PROCEDURES

In general, other than for partial dates, missing data will not be imputed and will be treated as missing. The algorithms for imputation of partial dates may vary depending upon the parameter.

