#### 9.9 STATISTICAL ANALYSES

## 9.9.1 PRIMARY EFFICACY VARIABLE - PFS

The two primary efficacy outcomes are overall response rate (ORR) and progression-free survival (PFS). Time to progression event "Survival" curve will be presented using Kaplan-Meier method. Median time to event and the 95% confidence interval of the median times will be presented, if estimable. Median time to event will be tested against the null hypothesis value using a one-sample (one-sided) log-rank test.

PFS is defined as the interval from Cycle 1, Day 1 to the earlier of the first documentation of definitive disease progression or death from any cause.

Overall Response Rate (ORR) will be determined according to the criteria of the International Workshop on Chronic Lymphocytic Leukemia (Hallek et al. 2018).

We will estimate Overall Response Rate (ORR), which is defined as percent of patients who achieve CR or PR. We will also estimate exact 95% confidence intervals for the response rates. These will be followed by additional logistic regression analyses model to adjust for demographic and baseline parameters.

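### Section 9.3 labels as ITT a set restricted by an undefined assessment requirement, no sentence fixes the ORR denominator, and 35 is used both as the number enrolled and as the number left from 40

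*Combined protocol and SAP*

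**What the plan says.** **Analysis set and denominator.**

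- Section 9.3 defines the efficacy set: "The ITT population will include all enrolled patients who provide some efficacy assessments". It gives no type, number or timing of assessment. The safety set in the same section is everyone who takes at least one dose.
- Section 9.7 begins its list of outcomes with "Each patient will be assigned to one of the following categories". The list covers complete and partial response, stable and progressive disease, three kinds of early death, and a residual class. It ends "7) early death because of other cause, or 8) unknown (not assessable, insufficient data".
- Section 9.8: "In general, other than for partial dates, missing data will not be imputed and will be treated as missing".
- Section 9.9.1 estimates "Overall Response Rate (ORR), which is defined as percent of patients who achieve CR or PR", with an exact 95% confidence interval. It does not say which patients form the denominator.
- Section 8.1: "All baseline assessments to characterize disease will be performed within 30 days of Cycle 1, Day 1, prior to initiation of therapy".
- Footnote 5 to the section 5 schedule says "CT imaging should be performed at EOT visit" when no scan was done in the preceding 30 days.

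**Sample size.**

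- The synopsis (Statistics row) says: "The study will plan to enroll up to 40 subjects, and assuming 10% attrition, there will be approximately 35 subjects remaining for analysis". Section 9.1 repeats this in nearly the same words.
- Both then give the Simon rule: 27 patients in stage 1, stop at 18 or fewer responses, otherwise add 8, and declare the regimen worthy of further study at 25 or more responses among 35 enrolled.
- Section 4.1 caps enrolment at 35.
- Section 9.1 allows screen failures to be replaced. No passage says whether an enrolled patient without an assessment is replaced.

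**The concern.** In a single-arm trial the response rate is the main result, so its denominator should be fixed before any data are seen. Here it depends on how an undefined phrase is read. Read as post-baseline, 9.3 removes the patients least likely to have responded (early deaths, withdrawals, losses) from a set still labelled ITT. Section 9.7 points the other way by giving those patients outcome categories, but it does not say that they count as non-responders.

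The decision rule counts patients enrolled. The published ORR, computed on the 9.3 set, could therefore rest on a different denominator from the go/no-go result. The two uses of 35 add to this: a number remaining for analysis suggests that unassessed patients are dropped, and a number enrolled suggests that they are not. As written, nobody can say with certainty which patients make up the 27 and the 35.

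**Working it through.** **Inputs.** Null and alternative ORR 0.60 and 0.80, error limits 0.10 each, stage 1 of 27 with a stop at 18 or fewer, total 35 with success at 25 or more, planned enrolment of up to 40 (all section 9.1 and synopsis), and the enrolment cap of 35 (section 4.1).

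**Step 1: reproduce the plan's design.** With X1 ~ Bin(27, p) and X2 ~ Bin(N − 27, p), and final cutoff c:

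P(success) = Σ over x = 19 to 27 of P(X1 = x) × P(X2 ≥ c − x)

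For N = 35 and c = 25 this gives 0.0965 at p = 0.60 and 0.900 at p = 0.80. Both limits are met. A grid search for the minimax design under these inputs returns the same bounds, so the design is not miscalculated.

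**Step 2: effect of 9.3 on the reported ORR.** Take 35 enrolled and 24 responders, one short of the rule. Let u patients have no post-baseline assessment; u is an assumption, since the documents give no figure for it. Reported ORR = 24/(35 − u), with exact (Clopper-Pearson) 95% limits:

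| u | ORR as reported | Exact 95% CI |
|---|---|---|
| 0, or baseline counts | 24/35 = 68.6% | 50.7 to 83.1 |
| 1 | 24/34 = 70.6% | 52.5 to 84.9 |
| 3 | 24/32 = 75.0% | 56.6 to 88.5 |

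The gain is 2.0 percentage points with one patient unassessed and 6.4 with three. The responder count stays at 24, so the trial still fails the rule in every row.

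**Step 3: effect of 9.3 on the decision rule.** Applied literally to 27 and then 35 enrolled, the rule counts responders. Removing a non-responder from the 9.3 set does not change that count, so the error rates stay as in step 1.

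**Step 4: effect of 35 against 40.** Stage 1 is unchanged and N = 40:

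| Final cutoff | Type I error | Power |
|---|---|---|
| 25 of 40 | 0.173 | 0.926 |
| 28 of 40 | 0.097 | 0.913 |

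The cutoff of 25 belongs to 35 patients and cannot be carried over to 40. A cutoff that meets both limits at 40 exists.

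**Step 5: cost of counting unassessed patients as non-responders.** If 0.80 was meant as a rate among assessed patients and a fraction a is unassessed, the effective rate is 0.80 × (1 − a). At N = 35 and c = 25:

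- a = 2.5%: rate 0.78, power 0.838
- a = 5%: rate 0.76, power 0.760

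**The case against.** The case against is substantial on size.

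- **9.7 and 9.9.1 together favour the strict reading.** Every patient gets a category, unknown is one of them, and ORR is a percentage of patients. This makes non-responder counting the more natural reading, and 9.8 does not contradict it. But it remains an inference, and 9.3 sets the population before 9.7 is applied.
- **Few dosed patients would have nothing post-baseline.** The schedule has examination and hematology on Cycle 1 Days 8 and 15 and an end-of-treatment CT. This stands. The plan's 10% attrition should not be equated with 10% unassessed, and the three-patient row above should be read as illustration only.
- **The two parts are separate.** The 35 against 40 conflict is independent of 9.3 and lends no weight to it. This also stands, and each part is judged on its own.

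Three stronger readings are tempting but unsupported.

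- A reader might infer that 9.3 inflates the type I error. That would need the rule to be applied to 35 evaluable patients drawn from a larger number enrolled, and 0.60 to be a rate among all enrolled. The documents state neither.
- A reader might infer that dropping patients carries the confidence interval past the 60% null. That depends on picking one particular combination of responders and exclusions, and the interval is not the decision criterion.
- A reader might object that 10% off 40 is 36, not 35. The plan says approximately 35, so this is rounding.

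**Conclusion.** The concern holds as two wording defects that need to be fixed.

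(A) The set that 9.3 calls ITT is not intent-to-treat on the post-baseline reading, and no sentence fixes the ORR denominator. The consequence is an upward shift in the reported ORR and its interval: near zero if baseline counts, and about 2 points for each patient dropped near the decision boundary. This assumes that those dropped are non-responders, as patients without a post-baseline assessment must be. The documents do not show how many there would be.

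(B) Whether 35 means enrolled or analysable patients is unsettled. The design is sound at 35. Type I error exceeds its limit only if more patients are counted against the unchanged cutoff, for example 0.173 at 40; the plan does not say that this will be done.

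Confidence is high in the gaps in wording. The sizes are conditional, as stated.

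**What to change.** 1. In 9.3, make the primary efficacy set all enrolled patients who take at least one dose, call it all-treated, and report how many were enrolled but not treated. Using all enrolled patients is an acceptable alternative and matches the wording of the rule in 9.1.
2. In 9.7 and 9.8, state that categories 5 to 8, and any patient with no post-baseline response assessment, count as non-responders for ORR and at both Simon stages.
3. Keep the assessed-only set as a secondary analysis, defined as at least one post-baseline response assessment.
4. Align the synopsis, 4.1 and 9.1 on one number. Apply the 18/27 and 25/35 bounds to the first 27 and the first 35 patients of the primary set. If more are to be counted, recompute the final cutoff; 28 of 40 with stage 1 unchanged is one that works.
5. State whether 0.60 and 0.80 refer to all patients in the primary set or to assessed patients only.

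**Cost.** This is wording only if 35 patients of the primary set are counted and both rates refer to that set. The reported ORR will be slightly lower than on the assessed-only set. If 0.80 was meant as a rate among assessed patients, the stated power must be restated using the figures in step 5.
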